**Table 1: Proposed Visit Schedule for TINSAL-T1DN Study**

Visit Number	Visit 1	Visit 2	Visit 3	Visit 4**	Visit 5	Visit 6**	Visit 7
Visit Description	Screening	Baseline	Monitoring	Monitoring	Monitoring/ Outcomes	Monitoring	Monitoring/ Outcomes
Time point	Day -180 to 0	Day 0	Month 1	Month 3	Month 6	Month 9	Month 12
Visit window		NA	± 7 days	± 14 days	± 14 days	± 14 days	± 14 days
Informed Consent	X						
Medical History /Physical Examination†	X	X		X	X	X	X
Laboratory Measures*	X			X	X	X	X
Skin Biopsies (proximal/distal leg)		X					X
Neurological History /Physical Examination†	X						X
Nerve Conduction Studies	X						X
Neuropathy Total Symptom Score	X	X			X		X
Cardiovascular Autonomic Studies		X					X
Resting Heart Rate		X	X	X	X	X	X
Quantitative Sensory Testing	X						X
NeuroQOL		X			X		X
Survey of Autonomic Symptoms		X			X		X
Neuropathy Pain Scale		X			X		X
Functional Assessments							
Berg Balance Scale							
8-foot Get Up and Go Test		X					
Modified Falls Efficacy Scale							X
Medication Dispensing§		X		X	X	X	
Medication Compliance			X	X	X	X	X
Medication Return				X	X	X	X
Adverse Events Monitoring		X	X	X	X	X	X

† Baseline history and examination will include diabetes duration, diabetes complications, diabetes treatment, concurrent medical problems, relevant past surgical history, height, weight, blood pressure and pulse, and foot examination. Follow up visits will include changes in medical or surgical history, weight, blood pressure, pulse and foot examination \* HbA1c, Metabolic Comprehensive Panel, Complete Blood Count with Platelets, TSH, Lipid Profile, Cystatin-C, Uric Acid and Urine Albumin performed at screening visit (unless results for these tests are documented in the medical record as being done in the prior 3 months for all except HbA1c (1 month) and Urine Albumin (6 months). Urine pregnancy test at screening for all women of childbearing potential regardless of contraceptive practiced. HbA1c, Metabolic Comprehensive Panel, CBCP, Cystatin-C, Uric Acid and Urine Albumin will be repeated at 3, 6, 9 and 12 months of follow-up. Lipids will be repeated at 3, 6 and 12 months of follow-up. Luminex inflammatory marker assays on blood and urine performed at screening or baseline, and again at study end.

\*Visit windows for visit 3-7 are based off when the patient starts the study medication following visit 2 due to the shipping of the medication from Belmar Pharmacy directly to the participant.

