### **6.1. Recruitment/Screening**

#### Visit 1: Screening/Eligibility

An eligibility visit will be scheduled for subjects who, based on preliminary screening (telephone, email, medical chart review) meet the general entry criteria (age, T1DM, diabetes duration, symptomatic peripheral neuropathy, no contraindications for salsalate, etc.). At visit 1 the investigator or her designee will obtain written informed consent, after which all required eligibility examinations will be performed. The eligibility examination will include the following laboratory assessments: HbA1c, metabolic comprehensive panel (METCOMP), complete blood count with platelets (CBCP), thyroid stimulating hormone (TSH), lipid profile, cystatin-C, uric acid, urine albumin assessment, and in all women of child bearing age and potential, a urine

pregnancy test, even if an accepted method of contraception is being used. If any of the required laboratory measures are documented in the subject's medical record as being completed in the prior 3 months (1 month for HbA1c, and 6 months for urine albumin), they will not need to be repeated at the screening visit. Additional blood and urine will be obtained for Luminex assays of inflammatory markers. The Luminex assays though may be postponed until the baseline examination.

Weight, height and seated blood pressure and pulse will be obtained.

A structured neurologic history and physical examination and nerve conduction studies will be performed at the screening visit to verify and document the presence of signs or symptoms of peripheral neuropathy, the presence of a sural nerve response, and abnormality of at least one abnormal nerve attribute (amplitude, latency, conduction velocity or f-wave) in the sural, peroneal or ulnar nerve. In the absence of a sural nerve response (e.g., sural amplitude is 0  $\mu$ V, response is unobtainable, then the presence of a peroneal motor nerve conduction velocity of  $\geq$  35 meters per second will be required for inclusion. Quantitative sensory testing will also be conducted at the screening visit.

All visit 1 measures are ideally to be completed within a 4-week time frame but may take up to 6 months (180 days) if repeated measures are needed, and may be done at one, or over several visits if that is more convenient for the subject.

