#### Analyses of Secondary Outcomes:

Due to multiple tests, formal statistical testing won't be performed; p-values will be reported to allow the reader to assess the result. For analysis of repeated measures of continuous data (change from screening/baseline to 12 months in NC studies, quantitative sensory testing, CAN measures, Neuropathy Symptoms, Pain, and NeuroQOL domain scores), a longitudinal approach will be employed. Specifically, each outcome will be analyzed using a mixed effect model for repeated measures with the treatment group and baseline HbA1c ( $\leq 8.0$  or  $> 8.0\%$ ) as fixed covariates. Under the model, time of assessment will be a continuous variable and the outcome will be modeled as a linear function of time. Appropriate non-linear parametric or non-parametric tests may be applied if assumptions of the model are not satisfied.

Logistic regression will be used to compare the proportion of subjects who have confirmed clinical neuropathy with NC and those who had normal NC and therefore required an assessment of IENFD for trial entry, between the salsalate and placebo groups, with covariates for treatment group, and baseline HbA1c ( $\leq 8.0$  or  $> 8.0\%$ ). The components of this composite endpoint will also be assessed. Rank-transformation analysis of covariance will be used on each of the NC values, and an overall treatment group differences in the multiple NC values will be assessed using the nonparametric Wei-Lachin rank test of stochastic order. The impact of additional covariates on the relationship between IENFD and confirmed clinical neuropathy and treatment will be explored by adding age, sex, height, weight, BMI, cigarette smoking, cardiovascular risk factors and concomitant medications into the models described above. A forward stepwise selection procedure will be used, with  $p < 0.10$  used to retain covariates. Interaction terms between treatment groups and select covariates will be investigated. In addition, we will adjust for the effect of changes in glucose on outcomes during the course of treatment by including HbA1c as a time-varying covariate in models.

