### **1. New subject enrollment**

Enrollment of new subjects (Screening Visit 1) may be paused until the investigator is notified that adequate supplies of study medications are available. Eligible participants who have not yet completed Visit 2 (randomization, assignment, and initiation of study medication) will have Visit 2 postponed. The protocol currently allows for Visit 2 to take place up to 180 days after Visit 1. If Visit 2 must be delayed for more than 180 days due to unavailability of study medication, then baseline laboratory measures performed at Visit 1 will be repeated at Visit 2. A delay of over 365 days would require that all Visit 1 screening measures be repeated prior to Visit 2. Reconsent of the participant would be required in this case.

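### For nerve conduction and quantitative sensory testing, a straight line in continuous time starting at screening is a poor estimator of the 12-month treatment effect; use a month-12 ANCOVA

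*Combined protocol and SAP*

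**What the plan says.** Section 10.2 (Analyses of Secondary Outcomes) lists the outcomes as "change from screening/baseline to 12 months in NC studies, quantitative sensory testing, CAN measures, Neuropathy Symptoms, Pain, and NeuroQOL domain scores". It then states that "each outcome will be analyzed using a mixed effect model for repeated measures with the treatment group and baseline HbA1c" stratum as fixed covariates, and that "Under the model, time of assessment will be a continuous variable and the outcome will be modeled as a linear function of time". The only alternative offered is conditional: "Appropriate non-linear parametric or non-parametric tests may be applied if assumptions of the model are not satisfied". The section does not say where time starts, whether dates are actual or nominal, whether treatment interacts with time, or which contrast is reported.

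The assessment times come from elsewhere:

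- **NC and QST.** Section 2 and Table 1 place them at screening and month 12 only. There is no Day 0 value.
- **Screening lag.** Table 1 allows screening from Day -180 to Day 0. Section 6.1 gives 4 weeks as the ideal for the Visit 1 measures, but says they "may take up to 6 months (180 days) if repeated measures are needed".
- **Clock for follow-up.** A Table 1 footnote says "Visit windows for visit 3-7 are based off when the patient starts the study medication following visit 2".
- **Supply disruption.** Under Appendix A, item 1, a gap of more than 180 days triggers repeat laboratory tests only. For the rest, "A delay of over 365 days would require that all Visit 1 screening measures be repeated prior to Visit 2".
- **Symptoms (NTSS).** Section 2 gives baseline and 12 months. Table 1 marks screening, Day 0, month 6 and month 12.

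**The concern.** For NC and QST the pre-treatment record and the month-12 record sit on different clocks. The interval between them is 12 months on treatment plus a drug-free lead that varies by subject. A straight line fitted over actual assessment time spreads the treatment difference across the whole interval, although no drug was taken in its first part. Read as a 12-month effect, such a slope is too small by an amount that depends on how long screening took and not on the drug.

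Section 10.1 says the trial is meant to supply preliminary data for designing a larger one, so the size of the NC and QST effects matters even without formal secondary tests. Cardiovascular autonomic measures, the pain scale and NeuroQOL have no screening record, so secondary effects could end up on different time scales.

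**Working it through.** The plan gives no figure for this point. Its one power figure (81%, Section 10.1) concerns the primary outcome and is not used here. For the record, a noncentral-t calculation with 25 per group, difference 1.65 and SD 2.0 gives 81.5%, so that figure reproduces.

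**NC and QST, two records.** Inputs: records at -s and 12 months, with s the screening lag in months (30.44 days each). Assumption: the between-arm difference is zero until Day 0 and equals D at month 12. The difference in slopes is then D/(12 + s), and scaled to 12 months it is

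D × 12/(12 + s).

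| Lag | s (months) | 12/(12 + s) |
|---|---|---|
| 28 days (ideal, Section 6.1) | 0.92 | 0.93 |
| 90 days | 2.96 | 0.80 |
| 180 days (maximum, Table 1) | 5.91 | 0.67 |
| 365 days (Appendix A) | 11.99 | 0.50 |

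The documents give no distribution of lags. If they were uniform over 0-180 days (an assumption), the pooled within-subject slope × 12 would be 12 × E(12 + s)/E[(12 + s)²] × D = 12 × 14.96/226.6 × D = 0.79 D. Uniform over 0-28 days gives 0.96 D.

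**Simulation check.** A random-intercept model with a treatment-by-time term was fitted to 60 simulated trials of 42 versus 28 subjects. D = 1; the assumed SDs were 2 between and 0.7 within subjects. Results: 0.63 (SE 0.02) at a 180-day lag, 0.80 (SE 0.02) with uniform lags, and 0.97 (SE 0.03) when the screening record was coded as time 0. The first is nearly two standard errors below the formula's 0.67; the other two agree with theory.

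**The model read literally.** With a treatment main effect and no interaction, the two-record model estimates the average of the arm differences at the two times, (0 + D)/2 = 0.5 D, whatever the lag. The simulation at 180 days gave 0.51.

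**Codings with no loss.** Nominal time with screening set to 0, a 12-month change score, or a contrast over the full fitted span, slope × (12 + s), each recover 1.00 D.

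**NTSS.** Least-squares slope × 12, as a share of D, on the Table 1 schedule:

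| Lag of Visit 1 | Effect linear to month 12 | Full effect by month 6 |
|---|---|---|
| 28 days | 0.96 | 1.05 |
| 90 days | 0.85 | 0.95 |
| 180 days | 0.70 | 0.80 |
| Visit 1 score left out | 1.00 | 1.00 |

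**Power.** At a common lag, two-record data shrink the slope estimate and its standard error by the same factor, so the test statistic does not change.

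**The case against.** The strongest reply is that Section 10.2 does not contain the biased estimator. The loss needs actual dates, a treatment-by-time slope and scaling to 12 months, and the text states neither the second nor the third. Describing the outcome as change from screening or baseline fits a coding that treats the screening value as time 0, which loses nothing. This stands: the understatement is conditional. But no loss-free coding is named as the model, and the literal main-effect reading gives about half the month-12 difference.

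Other points on that side:

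- **180 days is a ceiling.** Correct. At the 4-week ideal the loss is about 7%, and the 365-day case needs a long supply disruption.
- **NC has a second analysis.** Also correct. The rank-transformation ANCOVA and the Wei-Lachin test are not described as using time. They give no difference in natural units, however, and are not specified for QST.
- **No formal secondary testing is planned.** Correct; the point is about estimation.
- **Alternatives are allowed if assumptions fail.** This helps little, because two records per subject cannot reveal a bend at drug start.
- **Section 10 defers detail to a statistical analysis plan.** That is a suitable place for the correction, but the rule in 10.2 would still need to change.

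A reader might infer that symptoms are understated in the same way as NC and QST. The documents do not support that. NTSS has a Day 0 score, Section 2 names baseline as its start, nothing says the Visit 1 score enters the time trend, and if it did the bias could go either way.

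**Conclusion.** The point holds for NC and QST as a weakness of specification. A model linear in continuous time suits outcomes with one drug-free screening record and one month-12 record poorly. Scaled from an actual-date slope, it recovers about 93% of the 12-month difference at 4 weeks, 80% at 90 days, 67% at 180 days and 50% at 365 days under Appendix A. These figures assume that no difference arises before Day 0. The true lags are unknown, so the size is a range: from no loss to one third within the ordinary window, and up to half under Appendix A.

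A reader might go further and conclude that the planned analysis will understate these effects, or that power is lost. Neither follows: the plan leaves the time coding and contrast open, and the estimate and its standard error shrink together. NTSS is a secondary point, with bias possible in either direction.

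**What to change.** In Section 10.2:

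1. **NC and QST.** Replace the linear-in-time model with an ANCOVA of the month-12 value on treatment group, HbA1c stratum and the screening value as pre-treatment covariate. Report the adjusted month-12 difference. The plan already uses this structure in rank form for NC, and a similar one for the primary outcome.
2. **NTSS.** Name the Visit 2 (Day 0) score as baseline, keep the Visit 1 score out of the time trend, and report the month-12 treatment contrast.

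Moving time zero to the start of medication would not be enough, since shifting the origin changes no slope.

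The cost is a few sentences of analysis text, with no new visits, tests or subjects. The downsides are small: the Visit 1 NTSS is not used in the longitudinal model, and NC and QST are no longer analysed with a time slope, which two records could barely support.

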**Secondary outcomes:**

IENFD at the ankle at baseline and 12 months

Electrophysiological measures

- *Nerve Conduction Studies* of the sural, peroneal, and ulnar nerves will be obtained at screening and 12 months
- *Quantitative Sensory Testing*: Cold and Vibration thresholds are assessed at screening and 12 months.

- *Measures of CAN* will comprise cardiovascular reflex testing using the DCCT/EDIC protocol (R-R interval ratio during deep breathing, postural change, and Valsalva).

Clinical measures of DN will be assessed at baseline and 12 months and will include:

- a) *DN symptoms* as evaluated by the *Neuropathy Total Symptom Score-6 (NTSS-6)*
- b) *Survey of Autonomic Symptoms (SAS)*
- c) *The DCCT/EDIC Structured Neurological Examination*

Measures of DN- specific pain will include the pain domain part of the *NeuroQOL* and the *Neuropathic Pain Scale* that will be administered at baseline, 6, and 12 months.

Functional scales will be assessed at baseline and 12 months and include:

- a) *The Berg Balance Scale* which measures balance in 14 separate activities of daily living such as going from sitting-to-stand and standing on one leg; the unipedal stance portion that had been shown to be particularly reflective of neuropathy-related mobility loss;
- b) *The 8 Foot Up and Go Test*, a test of functional mobility that assesses the time needed for a subject to arise from sitting position, walk 8 ft. and turn 180 degrees around a cone and return sitting;
- c) *The Modified Falls Efficacy Scale* assessing patient's self-reported ability to perform activities of daily living (e.g. get dressed/ undressed, walking, shopping).

Quality of life measures will be administered at baseline, 6, and 12 months and include *the NeuroQOL*, a validated measure of quality of life specific to peripheral neuropathy.

**Exploratory outcomes:** will be assessed at baseline and 12 months and include:

- a) Assessment of expression of *pain-related molecules in distal leg skin biopsies*, including the ion channel TRPV1, TrkA receptors, and neuropeptides, e.g. substance P and CGRP, using our published protocol;
- b) *skin nerve fiber inflammatory markers* including TNF $\alpha$ , IL1 $\beta$ , CD68c, using our published protocol; and

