##### **4.1. Inclusion Criteria**

1. T1DM;
2. age 18-70;
3. mild DN as defined by symptoms and/or signs, confirmed by at least one abnormality in electrophysiology studies (abnormality of at least one attribute among conduction velocity, latency, amplitude or F-Wave in at least one nerve among sural sensory, ulnar sensory, or peroneal motor);
4. sural nerve amplitude  $> 0 \mu\text{V}$ . If sural nerve amplitude is  $0 \mu\text{V}$  (unrecordable) peroneal motor nerve conduction velocity must be  $\geq 35 \text{ m/second}^*$ ;
5. on a stable insulin regimen for the 3 months prior to enrollment;
6. be willing and capable of signing the IRB approved consent form and willing and able to cooperate with the medical procedures for the study duration;
7. be willing to accept random treatment assignment to salsalate or placebo; and
8. women of childbearing age agree to use an appropriate contraceptive method (hormonal, IUD, or diaphragm) for the duration of the study and must have a negative urine pregnancy test at screening.

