#### **10.1. Sample Size Determination**

The purpose of this clinical trial is to provide the preliminary data necessary to design a larger

multi-site clinical trial. There are two assumptions that are necessary to justify the larger trial. The first is that salsalate will cause an increase in nerve fiber density (re-innervation) and the second is that the natural progression of DN, even with treatment for diabetes, leads to loss of nerve fibers. The primary outcome is an assessment of IENFD at the distal thigh after 12 months of placebo or salsalate treatment.

In the largest study of IENFD, Lauria et al provided a table of median IEFND values in the distal leg as a function of age and gender. In the 20-29 age range the average IEFND was 12.2 fibers/mm with an average decline of 0.1 fibers/mm per year. We reported that the average IEFND in the distal leg in T1DM subjects (mean disease duration of 27 years) was 2.2 fibers/mm. If we assume that our diabetic subjects have the average IENFD for ages 20-29 shown by Lauria et al at the start of their disease, then the decline due to diabetes was 10 fibers/mm or an average of 0.25 fibers/mm /year. If the decline is more rapid as neuropathy progresses, then the average decline in IEFND may be as high as 0.5 fibers/mm/year.

In a study of the effect of physical exercise Smith et al found an increase in the IENFD at the thigh of 1.4 fibers/mm after one year of intervention. Based on our assumption about the mechanism by which salsalate will influence IEFND (reduction of inflammation), we believe that a similar increase in fiber density is possible with treatment with salsalate. In multiple studies that reported a change in IEFND over time (including one of our own studies), the standard deviation of the change was approximately 2 fibers/mm. With the above assumptions, there will be an expected difference of 1.65 fibers/mm ( $0.25 + 1.4 = 1.65$ ) in the change between the two groups at the thigh with a standard deviation of 2.0. With 25 subjects per group there will be 81% power to reject the null hypothesis of no difference between groups using a two-tailed t-test at a 5% level of significance. Prior data are insufficient to perform a power calculation for the distal leg.

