The trial will be considered a success if the primary endpoint demonstrates a significant difference between the two groups and one other secondary endpoint trends in a similar direction. This trial will also be considered a success if there is sufficient evidence to show that IEFND increases with salsalate but is likely to decrease with usual treatment. With 25 subjects per group, the standard error of the estimate will be approximately 0.4 [=2/square root (25)] and therefore the confidence interval for the mean change in each group will be the estimated mean change  $\pm$  0.8 fibers/mm; i.e. an increase of greater than 0.8 fibers/mm with salsalate and an observed decrease with placebo (since the expected decrease with placebo is not expected to be large). With these results, this trial would provide the preliminary data needed for a larger trial to validate the effect of salsalate. Assuming 15-20% attrition rates, 70 subjects will be recruited to attain the necessary 50.

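### The overall nerve conduction test, as named, takes no covariates, so it leaves unused the screening values that would sharpen it at no cost

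*Combined protocol and SAP*

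**What the plan says.** Section 10.2, Analyses of Secondary Outcomes, plans two layers for NC. For the components, "Rank-transformation analysis of covariance will be used on each of the NC values". For the summary, "an overall treatment group differences in the multiple NC values will be assessed using the nonparametric Wei-Lachin rank test of stochastic order". The reference list's entry for that method describes a two-sample test. (The in-text citation number, 102, does not lead to it: the list ends at 28.)

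Section 2 says that studies "of the sural, peroneal, and ulnar nerves will be obtained at screening and 12 months", so each subject has a screening value for each attribute recorded.

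Section 10.2 does not state:
- which NC attributes enter the overall test;
- whether month-12 values or changes are ranked;
- how attributes are oriented;
- any covariate for the overall test, or the covariates of the component analyses.

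Attributes are named only for eligibility and screening. Criterion 3 in Section 4.1 asks for "abnormality of at least one attribute among conduction velocity, latency, amplitude or F-Wave in at least one nerve".

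On inferential status, Section 10.2 says "Due to multiple tests, formal statistical testing won't be performed; p-values will be reported to allow the reader to assess the result". Section 10 defers detailed methods to a Statistical Analysis Plan to be finalized before the blind is broken.

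**The concern.** The overall test and the component analyses stand in one sentence but use the data differently. The components are analyses of covariance, for which the screening value is the natural covariate. The overall test, as named, compares two groups on ranks and uses neither the screening NC values nor the HbA1c stratum. An NC attribute at month 12 is likely to track its own screening value, so ignoring that value leaves between-subject variation in the error term.

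What is at stake is precision. An unadjusted overall test could look inconclusive where an adjusted one on the same data would show a consistent shift. NC is a listed secondary outcome, and one route to calling the trial a success in Section 10.1 requires that "one other secondary endpoint trends in a similar direction", so a clear reading of the NC outcomes has some use.

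**Working it through.** **1. The plan's own power figure.** It concerns intraepidermal nerve fiber density. Section 10.1 says "With 25 subjects per group there will be 81% power to reject the null hypothesis of no difference between groups using a two-tailed t-test". With a difference of 1.65, SD 2.0 and 25 per group, the noncentrality is (1.65/2.0) × √(25 × 25/50) = 0.825 × 3.536 = 2.917. The noncentral t distribution gives 81.5%, so the figure is reproduced. The plan gives no power, effect or correlation for NC, so the rest uses assumed inputs.

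**2. Inputs.**
- Completers: 70 recruited less 20% attrition (Section 10.1) leaves 56. Split 3:2 (Section 3) this is 33.6 and 22.4, taken as 34 and 22. Subjects enrolled before August 2017 were randomized 1:1, so the real split will be a little more even.
- Assumed: K = 10 attributes (amplitude, velocity and latency in three nerves, plus peroneal F-wave latency), all oriented so that higher is better; benefit d = 0.4 SD on each; between-attribute correlation ρ = 0.4; screening to month-12 correlation r = 0.5 to 0.8.

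**3. Normal approximation.** Let f = √(34 × 22/56) = 3.655. For a sum of K attributes with unit variance, the expected test statistic is:

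- Unadjusted month-12: z₀ = K·d·f / √(K[1 + (K−1)ρ]) = 4 × 3.655 / √46 = 2.155, power 58%.
- Ranked change: z₀ / √(2(1−r)).
- Adjusted for own screening value: z₀ / √(1−r²).

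| r | Unadjusted month-12 | Change | Adjusted |
|---|---|---|---|
| 0.5 | 2.155 (58%) | 2.155 (58%) | 2.489 (70%) |
| 0.8 | 2.155 (58%) | 3.408 (93%) | 3.592 (95%) |

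The ratio of adjusted to change is √(2/(1+r)): 1.155 at r = 0.5 and 1.054 at r = 0.8. Adjustment is never worse in this approximation, and its advantage over change shrinks as r rises.

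**4. Simulation with actual ranks, same inputs.** Over r = 0.5 to 0.8, power is 69-94% adjusted, 55-59% for unadjusted month-12 ranks and 58-91% for ranked change. At r = 0.6, 0.7 and 0.8 the adjusted test has 77%, 84% and 94%, against 64%, 77% and 91% for change. Rejection under no effect is near 5% for every version. The approximation runs slightly high, as expected when ranks replace normal values.

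**5. Orientation.** If 4 of the 10 attributes were left reversed, the mean of the sum would fall to (6−4) × 0.4 = 0.8 and its variance would be 10(1−0.4) + 0.4 × (6−4)² = 7.6. Then z = 0.8 × 3.655/√7.6 = 1.061, power about 19%. Simulation gives 18-19%.

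**6. Against a single component.** A single-attribute rank analysis of covariance has 36-60% power over the same range of r, against 55-59% for the aligned unadjusted overall test.

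**The case against.** Several objections carry weight.

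- **Ranked change is an ordinary reading.** Section 10.2 describes the NC outcome as change from screening when it introduces the mixed models. If changes are ranked, much of the precision is already recovered, and at r = 0.8 only about 3 points of power remain to be gained (94% against 91%). This stands, and it limits the size of the point.
- **Validity is not at issue.** The unadjusted test holds its type I error. Adjustment improves efficiency; it does not correct an error.
- **A separate Statistical Analysis Plan is still to come.** It could specify all of this. That makes it the place for the fix, but does not supply the specification.

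Three stronger readings are tempting and not supported:

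- A reader might infer that the plan adds up attributes pointing in opposite directions, since latency falls and amplitude rises as a nerve improves. The text never instructs that. A test of stochastic order presupposes a common orientation, and the attribute list comes from eligibility and screening rather than the analysis section. What is missing is a statement of sign coding.
- A reader might infer that the overall test is much weaker than the adjusted component analyses. Step 6 shows otherwise: once aligned, it is stronger than a single component or about equal.
- A reader might take this as the only planned summary of large-fiber function. Section 7.1.2 also has confirmed clinical neuropathy, which counts NC abnormality in at least two of three nerves, and Section 10.2 analyses it by logistic regression with HbA1c as a covariate.

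**Conclusion.** The point holds as a modest, inexpensive improvement. The overall NC test, as named, leaves the screening values unused. Adjusting for them raises power from 55-59% to 69-94% against unadjusted month-12 ranks, and from 58-91% to 69-94% against ranked change, with the smallest gain over change at the highest r. These figures depend on the assumed 0.4 SD benefit on every attribute, ρ = 0.4, r between 0.5 and 0.8, 10 attributes and 34/22 completers. None of the effect or correlation inputs is in the documents.

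The orientation statement is a clarification. It is worth making because an unaligned sum would largely cancel a real benefit, not because the plan calls for one. Since the p-values are descriptive and each NC value is analysed alongside the overall test, the priority is low.

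**What to change.** In Section 10.2 or the Statistical Analysis Plan, before unblinding, list the NC attributes to be analysed and add:

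> The overall NC test is the one-degree-of-freedom Wei-Lachin combination of the treatment effects from the rank analyses of covariance, each adjusted for its own screening value and the HbA1c stratum, using their joint covariance, over the same listed NC attributes as the component analyses. Latency-type attributes are multiplied by −1 so that higher is better.

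This also names the component covariates, which the current sentence omits. Correct the citation number for the test at the same time.

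The cost is a few sentences and a few lines of code. No new data are needed, because screening and month-12 NC values are already collected. The attribute list and sign coding should be fixed before unblinding, since choosing them afterwards could change the result.
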